The Montgomery-Asberg Depression Rating Scale (MADRS) (Montgomery and Asberg, 1979) and Quick Inventory of Depressive Symptomatology-Self Report version (QIDS-SR) (Rush et al., 2005; Rush et al., 2003) assessed the severity of depressive symptoms. The MADRS score was also used to stratify the randomization (MADRS > 19 for depressed group) as well as a secondary measure of depressive symptoms. The QIDS-SR assessed change in depressive symptoms during the trial. The QIDS-SR was administered during initial screening and during the Clinical Evaluation visits to track any change in depressive symptomatology. In addition, a physical pain score was obtained at baseline/screening and at every Clinical Evaluation. The participant was asked to rate overall physical pain in the last 24 hours on a scale of 0 to 10, with 0 corresponding to no pain and 10 corresponding to the most severe pain ever experienced. The Neurobehavioral Symptom Inventory (NSI) (King et al., 2012) assessed possible post-concussive symptoms associated with mild TBI. The scale is a 22 item self-report measure.

2.2.3 Evaluations: A safety assessment was performed prior to each treatment or at any time clinically indicated (e.g., significant side effect during or between treatments) consisting of asking about: 1) side effects, 2) changes in medication, 3) changes in medical conditions, and 4) changes in psychiatric symptoms (e.g., suicidality, plans to harm others). The Clinical Evaluations were performed after every 5 treatments for first 30 treatments, at the end of treatment taper, and at 1 and 3 month post-treatment follow-ups. The Clinical Evaluations consisted of PCL, QIDS-SR, and pain score on every evaluation visit. The IPF was obtained at baseline, after 15 treatments, after 30 treatments, at the end of treatment, and at the post

treatment 1 and 3 month follow-ups. CAPS, MADRS, and NSI were obtained at baseline/screening and after the 30th treatment.

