### **2.3 Data Analysis**

Data were double entered into an Access database and cross checked for discrepancies prior to analysis. Discrepancies were resolved by returning to primary sources. Descriptive

statistics were reported for the demographic and clinical characteristics of the obtained sample, including age, sex, education, employment, baseline function (IPF), baseline severity of PTSD (CAPS and PCL-5), baseline depression (QIDS-SR, MADRS), baseline pain (Pain Score), and baseline post concussive symptoms (NSI). Categorical variables were expressed as frequencies with percentages, and continuous variables as means with standard deviations. To assess how well the samples were randomized, the two active treatment groups were compared on baseline variables including demographics and the outcomes. No missing data imputation was performed. Chi-square tests and Fisher's Exact Test (whenever cell count is less than 5) were used to compare categorical variables; *t-tests were* used to compare continuous variables within and between groups.

For the primary hypothesis, a Welch two-sample t-test that assumes unequal variances was used to investigate whether 1 Hz rTMS versus 10 Hz rTMS provides a significantly greater improvement in PTSD symptoms (CAPS score) and/or function (IPF score) by 30th treatment. Improvement in an outcome was primarily defined as change in scores from pre-treatment baseline to post 30 treatments. The presence of a significant improvement from baseline to post 30 within each treatment group was also tested by performing a paired t-test.

Secondarily, improvement was also evaluated as the proportion of responders and remitters by post 30 treatments. Response was defined as score reduction of 50% (QIDS-SR and MADRS) or 30% (PCL-5 and CAPS-5). Remission was defined using the following score thresholds: 5 or less for QIDS-SR; 10 or less for MADRS; 33 or less for PCL-5; and no longer meeting criteria of PTSD on the CAPS-5. Other secondary analyses were similarly performed on QIDS-SR, pain, NSI, MADRS and PCL-5 scores.

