Additionally, sustainability of these treatment effects was investigated using loess (local least square regression), a non-parametric approach suitable for smoothing our numerical vector, of repeated observations. Loess fits least squares regressions to localized subsets of outcome data to produce graphical description of nonlinear empirical relationships (Jacoby, 2000). The graphical displays included smooth curves plus 95% confidence bounds which allowed us to evaluate a statistically significant difference between the mean trajectory over time versus its starting baseline score. We preferred the loess method to the simple pointwise plot of estimates of the mean for two reasons: addition of pointwise 95% confidence intervals will result in less efficient use of data compared to the loess estimates that are based on regressions in local neighborhood of each time point; and an alternative use of standard error of the mean around each estimate is not appropriate for inference as it underestimates the variability between individuals within the study sample (Diong et al., 2018; Nagele, 2003).

The proportions of side effects and dropouts per group were captured. Given the low proportions, a nonparametric binomial test was used to test for significant group difference in their proportions. Two-sided p-values were calculated and used to assess statistical significance defined as  $p < 0.05$ . All statistical analysis was carried out using the R statistical application.

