### **3.2 Effects at the end of 30 treatments**

The results of the two-sample t-tests failed to reject the null hypothesis of no significant difference between the two treatment groups (Table 2) in improvement on the CAPS ( $p = 0.77$ ) and IPF ( $p = 0.69$ ) scores from baseline to post-30.

- Table 2 about here –

The secondary analyses, however, yielded some significant findings with respect to the primary outcomes (Table 2). For the 1 Hz group, a paired t-test indicated that PTSD symptoms as measured by CAPS scores were significantly lower by the 30th treatment (improved,  $p = .03$ ). The scores on MADRS, PCL-5, and QIDS-SR also significantly improved. The change in function as measured by the IPF, however, did not quite reach significance ( $p=0.075$ ) in the 1 Hz group. In contrast, the 10 Hz group demonstrated significant improvement from baseline to the 30th treatment on all outcomes listed except pain score. (Table 2) Similarly, there was failure to reject the null hypothesis of no relationship between the groups on either response or remission rate by 30th treatment (Table 3).

- Table 3 about here –

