### **3.3 Effects at 3 months post treatment**

Figures 2 and 3 present trajectories of study outcomes using loess smooth curves (with 95% confidence bounds), which track changes in repeated assessment scores from baseline to 3 months post treatment. The top graph of Figure 2 fitted one trajectory to the whole sample (combined groups). It demonstrated that the average PCL-5 score declined below the lower 95% confidence limit of the baseline estimate (lower score is better) and stayed below this limit for up to 3 months post treatment.

The bottom graph (Figure 2) displays the loess curve split by group to investigate group difference in the trends. By showing overlap of their 95% confidence bounds everywhere the curves failed to reject the null hypothesis of no difference in the effects of 1 Hz versus 10 Hz rTMS treatments on PCL-5 over time. Similar patterns with equivalent interpretations for

depression symptoms (QIDS-SR) are shown in Figure 3. The loess curves for IPF and Pain score (not shown) also did not reveal a significant change in trend or treatment group difference.

- Figure 2 & 3 about here –

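### Sustainability is judged against the pre-treatment baseline, so the analysis shows that some improvement remains, not that the treatment-30 gain was kept

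*Combined protocol and SAP*

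**What the plan says.** Section 2.3 defines the effect first: "Improvement in an outcome was primarily defined as change in scores from pre-treatment baseline to post 30 treatments". It then says that the lasting of these effects is examined with loess curves and 95% bounds, whose purpose is to "evaluate a statistically significant difference between the mean trajectory over time versus its starting baseline score".

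Section 3.3 carries this out. The upper panel of Figure 2 "fitted one trajectory to the whole sample (combined groups"), and the "average PCL-5 score declined below the lower 95% confidence limit of the baseline estimate" and "stayed below this limit for up to 3 months post treatment". QIDS-SR is reported as similar. For the other two outcomes followed after treatment: "The loess curves for IPF and Pain score (not shown) also did not reveal a significant change in trend or treatment group difference".

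Under section 2.2.3, Clinical Evaluations took place after every five treatments up to 30, and "at the end of treatment taper, and at 1 and 3 month post-treatment follow-ups". CAPS, MADRS and NSI stop at treatment 30, so evidence on durability can come only from PCL-5, QIDS-SR, IPF and pain.

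**The concern.** The effect is a change from baseline to treatment 30. To ask whether it lasted is to ask how much of that change was still there later, and the natural reference is the score at treatment 30 or at end of taper, when treatment stops. The stated comparison uses the pre-treatment score instead. A curve that rebounds a long way but stays under the baseline limit passes, and no amount of lost gain is defined as a failure. This is separate from how the loess bounds are built: a fully valid test against baseline would have the same limitation.

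Section 3.3 is the only evidence on durability. IPF, which is part of the primary hypothesis, shows the consequence. In section 3.2, "the 10 Hz group demonstrated significant improvement from baseline" on every listed outcome except pain, and the 1 Hz group had p = 0.075 for IPF. Section 3.3 then finds no significant change in the IPF trend. Either function slipped back after treatment or the curve did not register the earlier gain, and a comparison with baseline cannot separate the two.

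**Working it through.** **Inputs from the documents.** Primary-endpoint completers: 14 (1 Hz) and 13 (10 Hz), total 27. One 10 Hz completer had no taper or follow-up visits, so 14 + 12 = 26 at 3 months (section 3.1). Post-hoc power for the CAPS-5 paired tests: 76% at 1 Hz and 98% at 10 Hz (section 3.5). CAPS at 1 Hz: p = .03 (section 3.2).

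**The plan's own figure.** No figure is stated for durability. The only related one that can be checked is the 76%. With p = .03 two-sided and n = 14, t = 2.44 and the standardised paired change is dz = 2.44/√14 = 0.65. Power is 61.6% two-sided and 74.6% one-sided, so 76% is matched closely only by a one-sided calculation. The 98% cannot be checked because Table 2 is not in the text available here.

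**Effect size used.** Inverting the stated powers gives dz of 0.66 and 1.09 (one-sided) or 0.77 and 1.22 (two-sided) for 1 Hz and 10 Hz. Weighted by group size:
- one-sided: (14 × 0.66 + 13 × 1.09)/27 = 0.87
- two-sided: (14 × 0.77 + 13 × 1.22)/27 = 0.99

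I use 0.85 to 1.0 and assume that it carries over from CAPS-5 to PCL-5.

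**Where the rule tips.** Let G be the treatment-30 gain in baseline SDs. With 27 at baseline, the lower limit lies 2.06/√27 = 0.396 SD below the baseline mean. The expected 3-month mean is below it if the fraction lost is less than 1 − 0.396/G:
- G = 0.5: 21%
- G = 0.75: 47%
- G = 1.0: 60%
- G = 1.2: 67%
- G = 1.5: 74%

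**Link from dz to G.** G = dz × √(1 + k² − 2rk), where k is the ratio of follow-up SD to baseline SD and r is their correlation. With k = 1 and r = 0.5, G = dz = 0.85 to 1.0. With k = 1 and r = 0.7, G = 0.775 × dz = 0.66 to 0.77. With k = 1.6 and r = 0.4, G = 1.51 × dz = 1.28 to 1.51. A ratio above 1 is plausible because entry required PCL-5 of at least 45, which narrows the baseline spread.

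**Chance of still passing, by simulation (dz 0.85 to 1.0).** The simple rule compares the raw 3-month mean (n = 26) with the baseline limit (n = 27). The loess rows assume 27 veterans at every visit, span 0.75, visits at weeks 0 to 6, 9, 13 and 22, equal SDs, and observations treated as independent when the bounds are built.

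| Setting | Half lost | Two-thirds lost |
|---|---|---|
| Simple rule, r 0.5, k 1 | 56-70% | 29-39% |
| Simple rule, r 0.7, k 1 | 35-49% | 15-21% |
| Simple rule, r 0.4-0.7, k 1.0-1.6 | 39-90% | 17-67% |
| Loess degree 2 on weeks, r 0.5 | 68-81% | 40-50% |
| Loess degree 2 on weeks, r 0.7 | 49-63% | 22-29% |
| Loess degree 1 on weeks, r 0.5 | 84-93% | 59-68% |
| Loess degree 1 on weeks, r 0.7 | 73-85% | 38-52% |
| Loess degree 1 on visit number, r 0.5-0.7 | 93-100% | 77-96% |

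The third row uses 1.96 for the limit. The first two use the t multiplier, which is why the second row reaches slightly lower.

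**What the direct contrast could do.** Take a paired t-test from treatment 30 to 3 months (n = 26, two-sided 0.05), and assume that this change has the same SD as the change from baseline. Power is 55-69% for a half loss and 79-90% for a two-thirds loss. The 95% half-width is 2.06/√26 = 0.40 SD of the change. Relative to the gain that is 0.40/1.0 = 40% to 0.40/0.85 = 47%.

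**The case against.** The baseline reference has a rationale. Section 2.3 defines improvement as change from baseline, so asking whether a change from baseline is still present later is consistent with it. The loess work is introduced as an additional, graphical analysis. The figures plot the whole course, so a rebound might be visible. Section 3.3 does not call the effect maintained; its wording is already close to saying that scores were still below baseline. These points stand. They confine the labelling problem to section 2.3, but they supply no estimate of what was retained, and the IPF and pain curves are not shown at all.

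A reader might infer that losing anywhere from half to two-thirds of the gain would usually pass. The documents do not support that. No PCL-5 mean, SD or correlation is visible, and under the simple rule with equal SDs a two-thirds loss passes in fewer than half of trials. The unstated smoother settings move the answer widely in both directions.

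A reader might also set the width of the baseline limit against the 30% response rule, which is at least 0.30 × 45 = 13.5 points at entry. That mixes the uncertainty of a group mean with a rule for classifying individuals, and the plan sets no such bar for mean change.

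Finally, the IPF result is not a case of the rule being lenient, since no significant change was reported. It shows only that the rule cannot answer the question.

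**Conclusion.** The point holds in this form: the comparison labelled as sustainability shows that some improvement over baseline remains at 3 months, and it cannot show that the treatment-30 gain was kept. That follows from the text and needs no assumptions.

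The size does need them. A half loss could often still pass, in roughly 39-90% of trials under the simple rule with dz 0.85-1.0, correlation 0.4-0.7 and SD ratio 1.0-1.6. A two-thirds loss passes in roughly 17-67%, and more often than not only if the gain was about 1.2 baseline SDs or more, or the smoother was stiff. The effect size is borrowed from CAPS-5.

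Nothing here shows that scores did rebound, or that the IPF gain was lost. The documents leave both open. The change should be made, but it does not affect the primary comparison of 1 Hz with 10 Hz.

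**What to change.** In section 2.3, add paired changes from treatment 30 and from end of taper to the 1- and 3-month visits for PCL-5, QIDS-SR, IPF and pain, in veterans with both visits (26 at 3 months). Report the mean change with its 95% confidence interval and, beside it, the share of the treatment-30 gain retained: (baseline mean − follow-up mean)/(baseline mean − treatment-30 mean) in the same veterans. This ratio is unstable where the gain is small, as it may be for pain.

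Base the durability statement on the estimate and interval. A non-significant contrast must not be read as maintenance, given 55-69% power for a half loss, and any retention margin chosen now would be post hoc and should be labelled so.

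Describe the existing loess comparison as showing scores still below baseline, not as sustainability. In section 3.3, state the retained IPF change explicitly.

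The cost is a few contrasts on scores already collected, plus wording. The downside is wide intervals with 26 veterans, so the durability statement may become weaker.

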### **3. RESULTS**

#### **3.1 Patient population**

Participant recruitment, enrollment, assignment to study conditions, and study retention are presented as a Consort diagram in Figure 1. Forty-four participants were enrolled with data

being acquired from September 2014 until February 2018. Nine veterans were not randomized with six failing to meet diagnostic criteria by CAPS-5, one was determined to have a history of seizures, one was unable to get off work, and one was unable to have motor threshold determined. Of the 35 randomized, 17 were allocated to the 1 Hz group and 18 to the 10 Hz group. Of the 17 veterans in the 1 Hz group, 14 completed the primary endpoint and all subsequent visits. The three participants who did not reach the primary endpoint included two that stopped due to work concerns and one who was lost to follow-up. Of the 18 veterans in the 10 Hz group, 13 completed the primary endpoints with one of those not completing the taper or follow-up visits. The five who did not reach the primary endpoint included two that could not tolerate the first treatment, one stopped due to headaches from another medical condition, one was too frustrated by parking, and one was lost to follow-up. A total of 27 who completed the primary end points constituted the final sample for testing the primary hypothesis, and they had no missing data on the tested outcomes.

- Figure 1 about here –

There were no significant differences between treatment groups on their baseline assessment scores, including demographic and baseline rating scales. (Table 1)

- Table 1 about here –

### **3.2 Effects at the end of 30 treatments**

The results of the two-sample t-tests failed to reject the null hypothesis of no significant difference between the two treatment groups (Table 2) in improvement on the CAPS ( $p = 0.77$ ) and IPF ( $p = 0.69$ ) scores from baseline to post-30.

- Table 2 about here –

The secondary analyses, however, yielded some significant findings with respect to the primary outcomes (Table 2). For the 1 Hz group, a paired t-test indicated that PTSD symptoms as measured by CAPS scores were significantly lower by the 30th treatment (improved,  $p = .03$ ). The scores on MADRS, PCL-5, and QIDS-SR also significantly improved. The change in function as measured by the IPF, however, did not quite reach significance ( $p=0.075$ ) in the 1 Hz group. In contrast, the 10 Hz group demonstrated significant improvement from baseline to the 30th treatment on all outcomes listed except pain score. (Table 2) Similarly, there was failure to reject the null hypothesis of no relationship between the groups on either response or remission rate by 30th treatment (Table 3).

- Table 3 about here –

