### **3.5 Post-hoc power calculations**

Given that the final group sample sizes of 14 and 13 (see Figure 1) used to test our primary hypothesis fell short of our anticipated evaluable sample of 40, inadequate statistical power was suspected. Therefore, post-hoc power calculations were performed based on the statistics obtained from the results of t-tests for CAPS-5 (Table 2). Using a paired samples t-test with alpha of 0.05, there were 98% and 76% power (for 10 Hz and 1 Hz groups respectively) to reject the null hypothesis of no difference between the baseline and post-30 scores (that the mean of the paired differences is zero); which support the conclusions reached from our significant results. For the nonsignificant results of 1 Hz versus 10 Hz, however, there was low power to

reject the null hypothesis of no difference in group means using a two-sided two-sample unequal-variance t-test with alpha of 0.05. Therefore, no definitive conclusion can be derived from any failure to reject the null (i.e. non-significant findings) in this study. Although we did not find a definitive conclusion with our study, the preliminary results are that if a difference exists at the group level, it is not likely a large clinical difference.

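### Up to fourteen within-arm paired tests at unadjusted 0.05 supply the positive treatment-30 claims after a null primary result, and the 1 Hz CAPS claim (p = .03) does not survive Holm once 1 Hz IPF is in the family

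*Combined protocol and SAP*

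**What the plan says.** In section 2.3 the primary-hypothesis paragraph assigns a Welch test to the comparison of 1 Hz with 10 Hz on "PTSD symptoms (CAPS score) and/or function (IPF score) by 30th treatment". The same paragraph then adds: "The presence of a significant improvement from baseline to post 30 within each treatment group was also tested by performing a paired t-test". The next paragraph covers response and remission and ends: "Other secondary analyses were similarly performed on QIDS-SR, pain, NSI, MADRS and PCL-5 scores". The significance rule comes at the end of 2.3: "Two-sided p-values were calculated and used to assess statistical significance defined as" p < 0.05. The document gives no testing order, alpha split or correction, and calls none of these tests exploratory.

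Section 3.2 reports the between-arm tests as null (CAPS p = 0.77, IPF p = 0.69) and continues: "The secondary analyses, however, yielded some significant findings with respect to the primary outcomes (Table 2"). For 1 Hz it reports CAPS (p = .03), MADRS, PCL-5 and QIDS-SR as significantly improved, and IPF as not significant (p = 0.075). For 10 Hz it reports every listed outcome except pain as improved.

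Section 3.5 states: "Using a paired samples t-test with alpha of 0.05, there were 98% and 76% power" for 10 Hz and 1 Hz respectively, "which support the conclusions reached from our significant results". Its warning against definitive conclusions covers only the non-significant results.

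**The concern.** With the randomised comparison null on both outcomes, the positive statements at treatment 30 all come from the paired tests. These are numerous, and each is judged as if it were the only test. They are planned inside the primary-hypothesis paragraph, called secondary once the primary has failed, tied back to the primary outcomes, and finally described as conclusions that power supports. No rule in the document lets this family be claimed at full alpha.

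What is at stake is the standing of the individual claims, above all improvement on the primary symptom scale in the 1 Hz arm. The problem remains even if the claim is only that scores changed, with no attribution to rTMS.

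**Working it through.** **Inputs from the documents.** Seven scales: CAPS and IPF (primary), QIDS-SR, pain, NSI, MADRS and PCL-5 (2.3). Two arms, n = 14 (1 Hz) and 13 (10 Hz) (3.5). Two-sided 0.05 per test (2.3). 1 Hz CAPS p = .03 and 1 Hz IPF p = 0.075 (3.2).

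**Not in the documents.** The correlation between scales is assumed, from 0 to 0.8. Table 2 is not shown, so its other p-values are unknown.

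**1. The document's own figure: 76% power for 1 Hz CAPS.** A two-sided p of .03 on 13 df gives t = 2.436. Using this as the noncentrality of a paired t-test with n = 14:
- two-sided alpha 0.05: 61.6% (58.7% to 64.9% over the rounding range of p);
- one-sided alpha 0.05: 74.6% (72.1% to 77.4%).

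The 76% is therefore reproduced only as a one-sided figure, whereas 2.3 specifies two-sided p-values. If 76% were two-sided, p would be about 0.0128, which contradicts the printed .03. Holm would then give 2 × 0.0128 = 0.026 in the smallest family below and 4 × 0.0128 = 0.051 over seven scales. I use the printed p. Either way, with n and alpha fixed, this power is a function of the observed p alone and adds no evidence.

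**2. Number of tests.** 7 scales × 2 arms = 14. Called significant: 4 at 1 Hz, and 7 − 1 = 6 at 10 Hz if Table 2 lists all seven scales, so about 10.

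**3. Chance of any false positive if no scale changed in either arm.**
- Independent tests: 1 − 0.95^14 = 51.2%.
- Equicorrelated scales, arms independent, by simulation: 1 − (1 − f₁)(1 − f₂), where f is the rate over the seven tests in one arm.
  - Correlation 0.3: about 47% (47.0% and 47.6% in two simulations).
  - Correlation 0.5: 1 − (1 − 0.237)(1 − 0.238) = 42%.
  - Correlation 0.8: 1 − (1 − 0.157)(1 − 0.156) = 29%.

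**4. Holm for 1 Hz CAPS.** At rank r of m, the adjusted p is at least (m − r + 1) × p. Because 1 Hz IPF has the larger p, CAPS cannot rank last in any family that contains it, so the multiplier is at least 2.

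| Family | Best rank | Adjusted p |
|---|---|---|
| 1 Hz CAPS and IPF | 1 of 2 | 2 × .03 = 0.06 |
| CAPS and IPF, both arms | 3 of 4 | 2 × .03 = 0.06 (0.09 if 10 Hz IPF p lies between .03 and .05) |
| Seven 1 Hz scales, NSI and pain non-significant | 4 of 7 | 4 × .03 = 0.12 or more |
| All 14, no assumption on unseen p-values | 13 of 14 | 2 × .03 = 0.06 or more |
| All 14, four non-significant as reported or inferred | 10 of 14 | 5 × .03 = 0.15 or more |
| The two CAPS tests only | 2 of 2 | 1 × .03 = 0.03 |

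If .03 is a rounding of .025, the smallest multiplier gives 2 × .025 = 0.050, which is still not below 0.05.

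**5. Benjamini-Hochberg for 1 Hz CAPS.** Over all 14 tests with ten significant: .03 × 14/10 = 0.042, provided the other nine p-values are at or below .03. Over the seven 1 Hz scales: .03 × 7/4 = 0.0525, or .025 × 7/4 = 0.044 at the lower rounding limit.

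**The case against.** A reader might draw four stronger conclusions, and the documents support none of them.

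- **That all fourteen tests are called significant.** About 10 are. Section 3.2 openly reports 1 Hz IPF and 10 Hz pain as not significant, and with Table 2 unseen the count of 14 is itself inferred.
- **That the 29% to 51% is the probability that the reported findings are false.** It is the chance of any false positive if nothing changed anywhere. The reported pattern hardly fits that scenario: in simulation under that null, 10 or more of 14 significant results occurred in none of 40,000 runs at correlation 0 or 0.5, and in about 0.08% at 0.8.
- **That the plan has no hierarchy.** Section 2.3 ties the primary hypothesis to the Welch test, and 3.2 reports that result first and calls the paired tests secondary. What is missing is error control or an exploratory label within that tier.
- **That no correction rescues 1 Hz CAPS.** Benjamini-Hochberg over 14 tests can, although it controls the false discovery rate rather than family-wise error. So can a CAPS-only family under Holm, but 2.3 names CAPS and IPF together and gives no basis for that family.

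It is also fair to say that PCL-5, another PTSD scale, is reported as improved at 1 Hz, and that adjusting the paired tests cannot alter the randomised comparison. The bound of 0.12 depends on NSI and pain being non-significant at 1 Hz, which 3.2 implies only by not naming them.

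These points narrow the concern without removing it. The paired results are still claimed without error control, and 3.5 still presents post-hoc power as support for them.

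**Conclusion.** The concern holds in this limited form. The paired tests are an uncontrolled secondary family that carries the positive treatment-30 message after a null primary result. The all-null error rate is 51% under independence and about 29% to 47% for assumed correlations of 0.8 to 0.3, against a nominal 5% per test.

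The specific casualty is 1 Hz CAPS. Its Holm-adjusted p is at least 0.06 in any family containing 1 Hz IPF, whatever the unseen p-values are, given the printed p of .03. The 10 Hz results are not shown to be wrong, and the between-arm conclusion is unaffected. The proper reading of 1 Hz CAPS is nominal significance that depends on the choice of family and method. The change should be made, but it concerns labelling and reporting and does not invalidate the trial.

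**What to change.** - **Section 2.3:** move the paired-test sentence out of the primary-hypothesis paragraph. State that the within-arm tests and the tests on the other scales are exploratory, with nominal p-values.
- **Section 3.2 and Table 2:** give within-arm mean changes with 95% CIs, and add a column of Holm-adjusted p-values over the seven scales in each arm. State that 1 Hz CAPS is nominally significant only and does not survive Holm.
- **Section 3.5:** delete the statement that post-hoc power supports the conclusions. If the power figures stay, state whether they are one-sided or two-sided and reconcile them with 2.3.

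The choice of Holm within each arm is a judgement. What matters is that the family and method are named and the nominal values are shown beside the adjusted ones.

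The cost is some rewording and one column computed from p-values and data already in hand. The downside is that some nominally significant secondary results become exploratory or non-significant.

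### Section 3.2 contrasts the arms on IPF by which within-arm paired test crossed 0.05, which is not evidence of a frequency effect; the direct comparison gives p = 0.69

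*Combined protocol and SAP*

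**What the plan says.** Section 2.3 makes the between-arm comparison primary: "a Welch two-sample t-test that assumes unequal variances was used to investigate whether 1 Hz rTMS versus 10 Hz rTMS provides a significantly greater improvement" on CAPS and/or IPF by the 30th treatment. It adds a second question: "The presence of a significant improvement from baseline to post 30 within each treatment group was also tested by performing a paired t-test". On the significance criterion it says "Two-sided p-values were calculated and used to assess statistical significance defined as" p below 0.05.

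Section 3.2 opens with the randomised comparison, which does not reject the null "in improvement on the CAPS ( $p = 0.77$ ) and IPF ( $p = 0.69$ ) scores from baseline to post-30". It then turns to the within-arm tests. For 1 Hz, "a paired t-test indicated that PTSD symptoms as measured by CAPS scores were significantly lower by the 30 th treatment" (p = .03), and "The scores on MADRS, PCL-5, and QIDS-SR also significantly improved", but IPF fell just short (p = 0.075). The next sentence begins "In contrast, the 10 Hz group demonstrated significant improvement" and covers all listed outcomes except pain. Response and remission rates did not differ between arms.

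Section 3.5 gives post-hoc power for the paired CAPS tests of 98% (10 Hz) and 76% (1 Hz), "which support the conclusions reached from our significant results". It also says that power for the between-arm test was low and that nothing definitive follows from the non-significant results.

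**The concern.** The trial asks whether 1 Hz and 10 Hz differ, and IPF is named in the primary hypothesis. The IPF miss under 1 Hz is followed at once by a contrast with 10 Hz. A reader may take this to mean that 10 Hz improved function and 1 Hz did not. A comparison of arms needs a test of the difference between them. Two separate tests against baseline can fall on opposite sides of 0.05 when the changes are nearly equal, and with 14 and 13 participants this happens often.

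The within-arm tests do not show efficacy either. Section 2.3 describes two active treatment groups, and section 3.1 places all 35 randomised participants in the 1 Hz or 10 Hz arm. (Section 2.2.4 mentions sham cards, but no sham arm appears in the design or the results.) A PCL-5 score of at least 45 was required at entry, so some regression to the mean is expected. Participants knew their assignment, and IPF and QIDS-SR are self-reported. Only completers were analysed: 14 of 17 and 13 of 18. Change from baseline therefore mixes treatment with all of these.

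**Working it through.** **Inputs.** Section 3.2: 1 Hz paired p = .03 (CAPS) and 0.075 (IPF); between-arm IPF p = 0.69. Section 3.5: n = 14 (1 Hz) and 13 (10 Hz); post-hoc power 76% and 98%. Section 2.3: two-sided, 0.05. Table 2 is not in the text available, so means and SDs are worked back from p-values.

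**1. The document's 76%.** CAPS p = .03 on 13 df gives t = 2.44, a standardised paired change of 2.44/√14 = 0.65. Power from the noncentral t with that noncentrality:
- two-sided 0.05: 61.6% (64.9% to 58.6% for an unrounded p of 0.025 to 0.035);
- one-sided 0.05: 74.6% (77.4% to 72.0%).

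So 76% agrees with a one-sided calculation and not with the two-sided convention of section 2.3; a two-sided 76% would need p of about 0.013. Section 3.5 does not state sidedness for the paired power. The 98% cannot be checked, because the 10 Hz p-value is not in the text. Either way, the power is a function of the observed p-value and adds nothing to it.

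**2. Between-arm IPF difference.** With equal SDs and 25 df, p = 0.69 gives |t| = 0.403.
- √(1/14 + 1/13) = 0.385.
- Difference = 0.403 × 0.385 = 0.155, about 0.16 SD of change.
- Half-width = 2.06 × 0.385 = 0.793.
- 95% CI about -0.64 to 0.95 SD. The text does not say which arm changed more.

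**3. Can p = 0.075 in one arm and p < 0.05 in the other coexist with p = 0.69 between arms?** For 1 Hz, t = 1.94 on 13 df. Let r be the ratio of the 10 Hz to the 1 Hz standard error of change. In units of the 1 Hz standard error, the difference is 0.404 × √(1 + r²), and the 10 Hz paired statistic is (1.94 ± difference)/r on 12 df.

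| r (assumed) | 10 Hz p if its change is larger | 10 Hz p if its change is smaller |
|---|---|---|
| 0.6 | 0.0017 | 0.031 |
| 0.75 | 0.007 | 0.081 |
| 1.0 | 0.028 | 0.197 |
| 1.25 | 0.061 | 0.323 |

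With equal standard errors and a larger 10 Hz change, the 10 Hz test is significant at p = 0.028. The difference is then 0.571/1.94 = 0.29 times the 1 Hz change, with a 95% CI of about -1.2 to +1.8 times that change. At r = 0.6 the 10 Hz test would be significant even if its mean change were the smaller one. The split therefore does not establish which arm improved more.

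**4. How often would the arms split by chance?** Assume the same true standardised paired change in both arms. Let p1 and p2 be the two-sided power of the paired test at n = 14 and n = 13. The chance that exactly one is significant is p1(1 - p2) + p2(1 - p1).

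| Assumed change | p1 | p2 | Exactly one significant | 10 Hz only |
|---|---|---|---|---|
| 0.3 | 0.180 | 0.169 | 29% | 14% |
| 0.4 | 0.284 | 0.264 | 40% | 19% |
| 0.5 | 0.410 | 0.382 | 48% | 23% |
| 0.6 | 0.547 | 0.512 | 50% | 23% |
| 0.7 | 0.678 | 0.640 | 45% | 21% |
| 0.8 | 0.790 | 0.754 | 35% | 16% |

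The observed 1 Hz IPF change, 1.94/√14 = 0.52, lies inside this range.

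**The case against.** The strongest reply is that the document never claims a frequency effect. The null randomised result comes first in section 3.2, and the null response and remission results follow the contrasting sentence. Section 3.3 says that the IPF curves showed no group difference. Section 3.5 rules out definitive conclusions from non-significant findings and thinks a large clinical difference unlikely. All of this stands. A reader who inferred that the authors conclude in favour of 10 Hz would go beyond the text.

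Nor were the arms opposed in general. A reader might infer that 10 Hz was significant and 1 Hz was not, but 1 Hz was also significant on CAPS, MADRS, PCL-5 and QIDS-SR. Only IPF is stated to be discordant. NSI is so by implication, being absent from the 1 Hz list, and pain is not reported as improved in either arm.

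The plan itself is not at fault. Section 2.3 lists the paired tests as an additional question about change from baseline and does not propose comparing arms through them.

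The power clause in section 3.5 concerns CAPS, where both arms were significant, so it is a related point and not an instance of the same fallacy. For that reason, 98% and 76% should not be put into the formula in step 4: they are unequal powers for an outcome on which the arms did not split.

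What remains is that the sentence compares arms by significance status on an outcome in the primary hypothesis. The section 3.5 disclaimer strengthens this, since it bars reading anything into the 1 Hz IPF miss, which is what the wording invites.

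**Conclusion.** The point holds for the IPF contrast in section 3.2. Differing within-arm significance is no evidence that the arms differ; a split of that kind would occur in roughly three to five of every ten such trials with identical true effects. This rests on the assumed standardised change of 0.3 to 0.8 and on independent arms. The direct estimate, about 0.16 SD (95% CI -0.64 to 0.95), rests on equal SDs and has unknown sign. It does not show that the arms are equivalent either; the interval allows a sizeable difference in either direction. The primary conclusion is unaffected, and what needs correcting is how the secondary results on IPF are read. Separately, the statement that post-hoc power supports the significant results should not stand, and the 76% appears to be one-sided.

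**What to change.** - Section 3.2: remove the contrasting phrase and report each arm's change without setting one arm's significance against the other's.
- Sections 2.3 and 3.2: base every statement comparing frequencies on the between-arm difference in change with its 95% CI, for each outcome. Add these to Table 2 if it lacks them.
- Keep the planned within-arm changes, shown as means with 95% CIs and labelled descriptive because there is no sham control.
- Section 3.5: delete the clause saying that power supports the conclusions. If the 76% is kept for any reason, state its sidedness and reconcile it with section 2.3.

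No new data are needed: the work is rewording and, at most, extra columns in one table. The downside is that fewer results are called significant.
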